TITLE The application of Hyperbaric Oxygen Therapy in Non-ventilated COVID-19 patients – Randomized Controlled Trial

INTRODUCTION

The 2019-20 coronavirus disease, caused by COVID-19, is an ongoing pandemic. The outbreak started in Wuhan, Hubei province, China, in December 2019 and the World Health Organization (WHO) recognized it as a pandemic on March 11, 2020. Up to Apr 9, 2020, there are more than 2 million confirmed cases, and over 140,000 deaths. In Israel, COVID-19 was confirmed in more 12,000 cases and took the life of 140 victims. There are 323 mild admitted cases, 170 moderate admitted cases and 170 severe admitted cases (16.04.2020).

Even though the general mortality rate is low (0.2-7%, country based), patients who develop Acute Respiratory Distress Syndrome (ARDS) have a significantly higher mortality rate, up to 61-90%]1[. COVID-19 ARDS is different, causing a rapidly progressive disease including respiratory insufficiency and pulmonary fibrosis]2[. The mechanism behind isn't clear yet, but evidence points to the direction of an acute cytokines storm which include: IL-2, IL-7, GCSF, InterferonGamma, TNF-alpha, Macrophage chemoattractant protein]3[. Poor prognosis include high levels of IL-6 and Ferritin]3[.

The SARS-CoV-2 virus is a positive RNA strand with the following structural proteins: Spike protein (S), Envelope protein ϵ , Membrane protein (M) and nucleocapsid. In addition the virus is encoded to several other protein: orflab, ORF1, OR3a, ORF6, ORF7a, ORF8 [4, 5]. A recent bioinformatic study analyzed the pathogenic function of these proteins. The study found the ORF8 protein and another glycoprotein are able to bind to the Porphyrin molecule (the ring surrounding the iron atom in the Heme component). Parallelly, the orflab, ORF10, ORF3a proteins are able to harm the HEME component. Located on the 1-beta chain of the hemoglobin molecule, unbinding the iron atom needed for the Porphyrin]6[.

More than 160 clinical trials have been registered, but as of April 2020, there is no proven effective treatment. In a recent randomized controlled trial including 199 patients, anti-viral drugs (Lopinavir-Ritonavir) did not show efficacy]7[. Moreover, the use of extracorporeal membrane oxygenation (ECMO) did not prove efficacy compared to the standard treatment on an analysis of 17 patients]8[.

BACKGROUND AND SIGNIFICANCE

The use of hyperbaric oxygen therapy (HBOT) includes breathing 100% oxygen in pressures higher than 1 absolute atmospheres (ATA), increasing the amount of oxygen dissolved in the plasma and the different tissues. During the session, oxygen partial pressure can increase from 100mmHg to 1700-2500mmHg (according to the applied pressure) [9]. In the last month, Chen et al. reported a case series of 5 severe COVID-19 patients treated with 3-8 HBOT sessions in addition to the standard therapy]10[. In all cases, they reported an increase in oxygen saturation, arterial oxygen content, lactate levels reduction, fibrinogen levels decrease and increase in lymphocytes number. In addition, the patients' chest CT showed improved signs. Symptomatic relief started following the 2nd session. No significant adverse events were reported [9].

These findings may be explained by the known physiological effects of HBOT, related to the SARS-CoV-2 virus pathogenesis:

- **Increased competitive binding of oxygen to the hemoglobin molecule**
 - it has been postulated recently the SARS-CoV-2 bind to the heme component in the hemoglobin molecule and reduces the oxygen affinity to hemoglobin. During HBOT, the increased amount of available oxygen molecules increases the binding to the hemoglobin molecules. This has shown significant beneficial effects in cases of another competitive molecule such as carbon monoxide intoxication, where HBOT induces carbon monoxide unbinding and release of the red blood cells [12, 11]. If the virus indeed affects the Heme component (as suggested above) in a competitive affinity, HBOT may significantly improve and normalize the red blood cells oxygen carrying capability.
- **Tissue oxygenation** – The oxygen content in the different tissues is multiplied by 25-30 times [13]. This effect has two therapeutic aspects: First, overcoming pulmonary hypoxia (either shunt or VQ mismatch) by increasing the FiO₂ significantly. By increasing the pulmonary oxygen gradient, oxygen diffusion increases and can overcome the inflammation in the alveoli and the thickened fibrosis caused by ARDS. These effects have been demonstrated in patients who developed ARDS after suffering a blunt chest trauma who were treated with HBOT. In these patients, HBOT induced improvement and rapid normalization of PaO₂, PaO₂/FiO₂ in addition to cardiac parameters CI and SVI]14[. Second, during HBOT, the amount of oxygen dissolved in the plasma

becomes significant and enables tissue oxygenation without the need of red blood cells]15[.

- **Mitochondrial function restoration** – HBOT can restore the normal function of the mitochondria and the cellular metabolism, decrease apoptosis and reduce the oxidative injury [16].
- **Anti-inflammatory** – HBOT reduces the following inflammatory cytokines both in the protein level and genes expression (mRNA): IL-2, TNF-alpha, IL-6, IL-1beta, mediated by several transcription factors: Hypoxia induced factor 1alpha (HIF1alpha), Nrf2, NFkB [17-19]. The anti-inflammatory effect has been shown in chronic diseases as well as models of acute infection and massive hemorrhage [20, 21].

Apart from Chen et al. case series, no prospective study was performed on the effect of HBOT on COVID-19 patients. In addition to the safety report in that case series, there's more evidence for the level of safety of HBOT in patients with acute pulmonary insufficiency:

- There is an ongoing debate in regards to the use of high inhaled oxygen level for patients with ARDS. In a recent randomized controlled trial (LUNGSafe), there was no association between high oxygen levels and bad prognosis]22[.
- The use of HBOT in patients with ARDS after blunt chest trauma, showed promising results in oxygenation and cardiac function, with no safety issues]14[.

STUDY OBJECTIVES

The purpose of the current study is to evaluate the efficacy of HBOT in moderate-severe non ventilated COVID-19 patients.

The primary objectives of study will be to assess the following indicators:

- Oxygenation index = $\text{PaO}_2/\text{FiO}_2$ one day after the last session.
- SpO_2 – room air saturation one hour before and after a session, 6 hours after a session and one day after the last session.
- NES – Early warning score, before and after each session, 6 hours after each session and one day after the last session
- Inflammatory parameters one day after the last session: WBC, Immune profile, CRP, ESR, Procalcitonin, TNFalpha, IL1, IL2, IL6, IL10.

The secondary objectives of study will be to assess the following indicators:

- Oxygenation index = PaO₂/FiO₂ one week after the last session.
- SpO₂ – room air saturation one week after the last session.
- NES – Early warning score, one week after the last session
- Inflammatory parameters one week after the last session: WBC, Immune profile, CRP, ESR, Procalcitonin, TNF_{alpha}, IL1, IL2, IL6, IL10.
- Symptoms level one day and one week after the last session
- Viral load one day and one week after the last session
- Chest Xray changes one day and one week after the last session
- Percentage of patients with positive IgG serology one day and one week after the last session
- Percentage of patients with positive IgM serology one day and one week after the last session
- Pulmonary function test one day and one week after the last session
- Time to symptoms recovery
- Percentage of patients who required invasive intubation
- Time to recovery (negative PCR twice) – TTCR
- Mortality rate in 30 days
- Safety – percentage of adverse events

STUDY DESIGN

Subjects: Patients at Maimonides Medical Center (MMC)

Eligibility Criteria:

Patients who are (1) within 7 days of need of oxygen supply, (2) positive to SARS-CoV-2 through RT-PCR, (3) have at least one risk factor for bad prognosis of COVID-19: hypertension, diabetes mellitus, ischemic heart disease, smoking, age>50, etc., (4) have respiratory insufficiency: Room Air SpO₂ <94% or PaO₂/FiO₂<300mmHg, (5) are older than 18 years of age and (6) have ability to sign an informed consent will be included in the study.

Patients who are (1) negative to SARS-CoV-2 through RT-PCR, (2) have a HBOT contraindication: pneumothorax, pneumomediastinum, claustrophobia, ear/sinus disease which aren't allowed in HBOT, known chronic pulmonary disease: severe emphysema or known pulmonary bullae, (3) have pregnancy and/or (4) have inability to sign an informed consent will be excluded from study.

Design:

This study is a prospective randomized controlled, double blind clinical trial performed on laboratory confirmed COVID-19 infection admitted patients in MMC. It involves the use of MMC monoplace HBO chambers. The trial will include 30 patients who will undergo either hyperbaric oxygen therapy (HBOT) or Normobaric oxygen therapy (NBOT), randomized on a 2:1 ratio, within 4 days in addition to the standard treatment including oxygen, drugs, steroids, bronchodilators, antibiotics and others.

The evaluation procedure includes symptom monitoring, room air saturation, vital signs monitoring, pulmonary function and blood tests at baseline, one day and one week after the last session. In addition, one hour prior to and post session saturation and vitals will be monitored.

Data Collection Procedures:

Upon signing an informed consent, the patients will be randomized 2:1 to hyperbaric oxygen therapy group (HBOT) and normobaric oxygen therapy group (NBOT) (Randomization will be performed using a computer software based on patient id). Following the randomization, the patients will undergo evaluation including symptoms, vitals, pulmonary function, blood tests.

The patients will undergo 8 sessions of either hyperbaric/normobaric oxygen therapy, 2 sessions per day, in 4 consecutive days. During the sessions, the symptoms and vitals will be monitored. 1 day and 1 week following the last session, reevaluation will be performed.

Protocol Day 1

1. Baseline evaluation: blood test including: arterial blood gases, 2 CBC tubes, 2 Gel tubes (10-15 cc total), vitals (temperature, blood pressure, heart rate, room air saturation), symptoms questionnaire, pulmonary function test.
2. Vitals (temperature, blood pressure, heartrate, room air saturation) one hour prior to session
3. One-hour session NBO/HBO
4. Vitals (temperature, blood pressure, heartrate, room air saturation) one hour after the session.
5. Vitals (temperature, blood pressure, heartrate, room air saturation) one hour before the 2nd session.
6. One-hour session NBO/HBO (8 hours following the first session)
7. Vitals (temperature, blood pressure, heartrate, room air saturation) one hour after the session.
8. Daily oxygen supply dose monitoring.

Protocol Day 2-4

1. Daily symptoms questionnaire
2. Vitals (temperature, blood pressure, heartrate, room air saturation) one hour prior to session
One-hour session NBO/HBO
3. Vitals (temperature, blood pressure, heartrate, room air saturation) one hour after the session.
4. Vitals (temperature, blood pressure, heartrate, room air saturation) one hour before the 2nd session.
5. One-hour session NBO/HBO (8 hours following the first session)
6. Vitals (temperature, blood pressure, heartrate, room air saturation) one hour after the session.
7. Daily oxygen supply dose monitoring.

Follow up Protocol

1. Repeat evaluations one day after the last session and one week after the last session:
 - Blood test including: arterial blood gases, 2 CBC tubes, 2 Gel tubes (10-15 cc total)
 - Vitals (temperature, blood pressure, heart rate, room air saturation)
 - Symptoms questionnaire
 - Pulmonary function test.
2. Oropharyngeal swab for SARS-CoV-2 RT-PCR every 3 days for 1 week
3. Clinical monitoring for 30 days

Data Analysis:

Continuous data will be expressed as means \pm standard-deviations. Independent and dependent t-test with two-tail distribution will be performed to compare variables between and within the two groups, when a normality assumption holds according to Kolmogorov-Smirnov test. Categorical data will be expressed in numbers and percentages and compared by chi-square tests. Univariate analyses were performed using Chi-Square/Fisher's exact test to identify significant variables. A value of $p<0.05$ will be considered significant.

Data analysis will be performed with Matlab R2019b (Mathworks, Natick, MA) Statistics Toolbox.

Sample Size: 30

Based on a previous study on HBOT effect on ARDS [14], with 95% power and significance level of 5%, and a groups difference of 30 (SD 15-18) in the PaO₂/FiO₂ and a 2:1 groups allocation, the sample requires 7 NBOT patients and 13 HBOT patients. Considering 15% dropout, we will recruit 10 NBOT patients and 20 HBOT patients, 30 in total.

Expected Outcomes:

The primary outcomes measures that will be accessed in the study are:

- Oxygenation index = PaO₂/FiO₂ one day after the last session.
- SpO₂ – room air saturation one hour before and after a session, 6 hours after a session and one day after the last session.
- NES – Early warning score, before and after each session, 6 hours after each session and one day after the last session
- Inflammatory parameters one day after the last session: WBC, Immune profile, CRP, ESR, Procalcitonin, TNF α , IL1, IL2, IL6, IL10.

The secondary outcomes measures that will be accessed in the study are:

- Oxygenation index = PaO₂/FiO₂ one week after the last session.
- SpO₂ – room air saturation one week after the last session.
- NES – Early warning score, one week after the last session
- Inflammatory parameters one week after the last session: WBC, Immune profile, CRP, ESR, Procalcitonin, TNF α , IL1, IL2, IL6, IL10.
- Symptoms level one day and one week after the last session
- Viral load one day and one week after the last session
- Chest Xray changes one day and one week after the last session
- Percentage of patients with positive IgG serology one day and one week after the last session
- Percentage of patients with positive IgM serology one day and one week after the last session
- Pulmonary function test one day and one week after the last session
- Time to symptoms recovery
- Percentage of patients who required invasive intubation
- Time to recovery (negative PCR twice) – TT_{CR}
- Mortality rate in 30 days
- Safety – percentage of adverse events

Timetable: 12 months

Adverse Event Reporting

Subjects will be monitored for adverse events (AEs) during the entire study and more particularly, during and after each treatment session by clinical inquiry, clinical observation and (when applicable) by clinical examination. AE information will be documented and all subjects will be questioned about AEs at each visit during the treatment period and at the follow-up visits. AEs will also be recorded whenever spontaneously reported by the subject. Event description, date of onset, intensity,

duration, treatment for AE, whether the AE was resolved and probable relationship to the study product will be recorded onto case report forms (CRFs).

The investigator must record all serious adverse events regardless of treatment or relationship to investigational product as soon as s/he is informed of the event.

Any serious adverse event (SAE) which occurs after a patient has entered the study (after signing informed consent), must be reported. The original copy of the serious adverse event form must be kept with the documentation at the site.

Patients who have had an SAE during the treatment period must be followed clinically until all parameters (including laboratory), have either returned to normal, have stabilized or are otherwise explained.

SAEs should be reported by the investigator to competent authorities and ethics committees according to local requirements.

For more information, see research protocol from overall study.

REFERENCES

1. Goh, K.J., et al., *Rapid Progression to Acute Respiratory Distress Syndrome: Review of Current Understanding of Critical Illness from COVID-19 Infection*. Ann Acad Med Singapore, 2020. **49**(3): p. 1-9.
2. Mehta, P., et al., *COVID-19: consider cytokine storm syndromes and immunosuppression*. Lancet, 2020. **395**(10229): p. 1033-1034.
3. Ruan, Q., et al., *Clinical predictors of mortality due to COVID-19 based on an analysis of data of 150 patients from Wuhan, China*. Intensive Care Med, 2020.
4. Zhu, N., et al., *A Novel Coronavirus from Patients with Pneumonia in China, 2019*. N Engl J Med, 2020. **382**(8): p. 727-733.
5. Wu, F., et al., *A new coronavirus associated with human respiratory disease in China*. Nature, 2020. **579**(7798): p. 265-269.
6. Liu, W. and H. Li, *COVID-19: Attacks the 1-Beta Chain of Hemoglobin and Captures the Porphyrin to Inhibit Human Heme Metabolism*. 2020.

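### Background steroids, antibiotics and other drugs are neither recorded in the schedule nor used in the analysis of the primary inflammatory markers: a loss of precision at baseline, and undetected bias if later use differs by arm

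*Combined protocol and SAP*

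**What the plan says.** The Design paragraph of the combined protocol and SAP gives both study treatments "in addition to the standard treatment including oxygen, drugs, steroids, bronchodilators, antibiotics and others". It fixes no agent, timing or rule for these drugs.

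Expected Outcomes lists among the primary outcomes "Inflammatory parameters one day after the last session: WBC, Immune profile, CRP, ESR, Procalcitonin", followed by TNF-alpha and four interleukins.

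Protocol Day 1, Protocol Day 2-4 and Follow up Protocol itemise blood tubes, vital signs, symptoms, pulmonary function and swabs. The only co-treatment in these lists is oxygen: "Daily oxygen supply dose monitoring". The follow-up entry, "Repeat evaluations one day after the last session and one week after the last session", has no medication item. Adverse Event Reporting puts one drug-related field on the case report form, limited to events: "duration, treatment for AE, whether the AE was resolved and probable relationship to the study product will be recorded onto case report forms".

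Data Analysis states: "Independent and dependent t-test with two-tail distribution will be performed to compare variables between and within the two groups". It adds univariate chi-square or Fisher's "exact test to identify significant variables", but no model follows and no covariate is named. On allocation, Data Collection Procedures says "Randomization will be performed using a computer software based on patient id", with no stratification. The trial is called double blind, but no sham or masking procedure is described.

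**The concern.** If steroids or antibiotics act on the markers in the primary panel, differences in their use between arms add to, or subtract from, whatever HBOT does. The documents give neither a rate of use nor a drug effect on any marker, so both are assumptions here. The Background section rests part of the rationale on HBOT lowering cytokines that also sit in the primary panel, so the marker result will be read as evidence of mechanism.

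Two routes must be kept apart. Use before the first session can be unbalanced by chance, which matters with only 10 NBOT patients. Use that begins after randomisation can differ systematically, either because treating staff know the arm or because patients respond differently. As the schedule stands, the trial data would show neither.

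**Working it through.** **The plan's own figure.** The sample size (7 NBOT + 13 HBOT evaluable, 30 recruited) is for PaO2/FiO2: difference 30, SD 15-18, two-sided 5%, 95% power. Exact t-test power for 7 + 13 is 98.1% at SD 15, 95.6% at SD 16.5 and 91.9% at SD 18, so the figure reproduces near the middle of the SD range. It says nothing about the inflammatory markers, for which no effect or SD is given.

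**Inputs.** From the documents: 20 HBOT, 10 NBOT, unstratified, unadjusted two-sided t-test at 5%. Assumed: steroid use 30-70% (20-80% for power), steroid shift 0 to 1.5 SD of a marker, HBOT effect 1.2 SD.

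**Step 1: chance imbalance at baseline.** If K of 30 patients are on steroids and a of them fall in HBOT, the gap is a/20 - (K - a)/10 = (3a - 2K)/20, and a is hypergeometric.
- Gap of 25 points or more: 20-26% at every K from 9 to 21.
- Gap of 30 points or more: 20-25% when K is 9, 12, 15, 18 or 21, and 10-12% at the other counts. The jump arises because a gap of exactly 6/20 needs 3a = 2K ± 6, which is possible only when K is a multiple of 3.
- Treating each patient's use as random instead (binomial), a gap of 30 points or more has a 12% chance at 30% or 70% use and 16% at 50%.

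**Step 2: does baseline use bias the test?** With 50% use in both arms, no HBOT effect and a shift of 0.5, 1.0 or 1.5 SD, the simulated rejection rate of the planned t-test is 4.9-5.1%. It does not.

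**Step 3: precision.** Simulated power for a 1.2 SD HBOT effect, 20 v 10, without and with a yes/no term for baseline steroid use:

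| Steroid shift | Example (50% use): unadjusted to adjusted | Change over 20-80% use |
|---|---|---|
| 0.25 SD or less | about 85% to 84% | about -1 point |
| 0.5 SD | 83% to 83-84% | 0 to +1 |
| 1.0 SD | 76% to 83% | +4 to +8 |
| 1.5 SD | about 67% to 83-84% | +11 to +17 |

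These figures do not include any gain from the baseline marker value.

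**Step 4: starts after randomisation that differ by arm.** With no HBOT effect, the expected difference is shift × (difference in use). For 70% NBOT v 40% HBOT at 1 SD it is 1 × (0.70 - 0.40) = 0.30 SD. The variance of the difference is (1 + 0.4 × 0.6)/20 + (1 + 0.7 × 0.3)/10 = 0.062 + 0.121 = 0.183, so the standard error is 0.43 and the ratio is 0.30/0.43 = 0.70. Simulated rejection rates of the 5% test:
- 1 SD shift: 7.4% (60% v 40%), 10.4% (70% v 40%), 14.6% (80% v 40%).
- 0.5 SD shift: about 6% at both 60% v 40% and 70% v 40%.

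**The case against.** The strongest reply is that randomisation deals with the problem. For drugs in use at baseline this stands: imbalance is by chance, the t-test already allows for it, and Step 2 confirms the 5% error. A reader might infer from the missing record that the inflammatory comparison measures drug use rather than HBOT. The documents do not support that. For baseline use the cost is precision only, and for later use bias is possible but not shown.

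It can also be said that the precision gain depends on the assumed shift. This is true: at 0.5 SD there is almost nothing to gain, and at 0.25 SD or less the extra term costs about 1 point. The case for the covariate is that the possible loss is small and the possible gain is not.

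Differential starts are hypothetical, and the protocol does call the trial double blind. But no masking procedure is described, so knowledge of the arm cannot be ruled out. Even with effective masking, patients who respond differently may be given different drugs.

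Finally, these are inpatients, so drug use could probably be recovered from the charts later. It would therefore be too strong to say that it could never be known. What stands is that the plan neither collects it nor says how it would be used. Adverse Event Reporting also refers to an overall-study protocol that is not supplied. It may contain a medication record, but the pointer concerns adverse events and does not alter the unadjusted analysis given here.

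**Conclusion.** The point holds in a limited form and should be acted on, but it does not invalidate the trial. Background drugs are unrecorded in the schedule and unused in the analysis, while inflammatory markers are primary.

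For use before the first session, the consequence is lost precision and an imbalance that would go unreported: a 20-26% chance of a gap of 25 points or more, and 10-25% for 30 points or more depending on the count (12-16% unconditionally). It would be tempting to quote 20-25% for the 30-point gap, but that applies only when the number on steroids is a multiple of three.

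For drugs started after randomisation, the consequence is possible bias that the planned data would not reveal: about 7-15% rejection at an assumed 1 SD shift, and about 6% at 0.5 SD. All of these sizes rest on assumed rates of use and assumed drug effects; the 20 v 10 allocation and the unadjusted test come from the documents.

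**What to change.** 1. Add one line to the baseline, daily and follow-up lists under Data Collection Procedures: use of steroids, immunomodulators, antibiotics and bronchodilators, with start and stop dates, taken from the inpatient drug chart.
2. Prespecify that each inflammatory marker is compared between arms with a linear model containing arm, the baseline marker value and baseline steroid use (yes/no, before the first session). The baseline blood tubes match those at follow-up, so no new sample is needed.
3. Tabulate drugs started after randomisation by arm. Do not adjust for them, because treatment may affect them. If the arms differ, qualify the conclusion on the markers. This makes the problem visible; it does not remove it.

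Cost: one case-report-form line and one degree of freedom for steroid use (error degrees of freedom from 28 to 27 with 30 patients, and 26 with the baseline marker value as well), with no extra visit. If steroids have little effect on a marker, about 1 point of power is lost.

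### Allocation rests on patient id, with no concealment or blocking described and baseline measured after randomization: a risk of selection and baseline-assessment bias, and an unsecured 10:20 split

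*Combined protocol and SAP*

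**What the plan says.** Study Design, Data Collection Procedures, has patients randomized 2:1 to HBOT or NBOT once they have signed consent. On the method it says only: "Randomization will be performed using a computer software based on patient id". The next sentence is: "Following the randomization, the patients will undergo evaluation including symptoms, vitals, pulmonary function, blood tests".

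The Design paragraph repeats the 2:1 ratio and gives the blinding label: "This study is a prospective randomized controlled, double blind clinical trial". It does not say how blinding is achieved.

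The Sample Size section treats the arm sizes as fixed. For evaluable patients, "the sample requires 7 NBOT patients and 13 HBOT patients". After an allowance for 15% dropout, "we will recruit 10 NBOT patients and 20 HBOT patients, 30 in total".

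The document does not say how the sequence is generated, whether it is blocked or stratified, who holds it, or how the next assignment is kept from recruiters. Nor does it say whether the id is a hospital number that exists before consent or a study number issued at enrolment, or how the id leads to an arm.

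**The concern.** Three things follow from this wording.

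- **Selection.** An arm computed from an identifier is protected only if recruiters cannot know the identifier and the rule beforehand. With 10 planned controls, a few steered enrolments could shift a mean. Eligibility leaves some room for discretion, because the list of qualifying risk factors is open-ended.
- **Baseline assessment.** The baseline evaluation follows assignment. It includes a symptoms questionnaire and pulmonary function tests, which depend on patient effort and on how staff ask or coach. Baseline also enters the analysis directly: Data Analysis plans within-group as well as between-group tests ("Independent and dependent t-test with two-tail distribution will be performed"), so a baseline shaped by knowledge of the arm carries into the measured change.
- **Arm sizes.** A 2:1 ratio is not a 10:20 count. Without a restriction, the counts in the Sample Size section are expected values.

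**Working it through.** **Inputs from the documents.** Difference 30 in PaO₂/FiO₂, SD 15 to 18, 95% power, 5% significance, 2:1 allocation, 7 + 13 evaluable, 15% dropout, 10 + 20 recruited (Sample Size); two-tailed t-test (Data Analysis).

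**Assumptions.** For the arm-size calculation, the software acts as independent draws with probability 1/3 for NBOT. Dropout is random at 15% in both arms.

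**1. The plan's own figure.** The normal formula for the smaller arm is n = (1 + 1/2) × (1.960 + 1.645)² × (SD/30)².
- SD 15: 4.9, so 5 + 10
- SD 16.5: 5.9, so 6 + 12
- SD 17: 6.3, so 7 + 14
- SD 18: 7.02, so 8 + 16

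By the exact (noncentral) t, 7 + 13 has power 98.1% at SD 15, 95.6% at SD 16.5 and 91.9% at SD 18. The stated 20 reproduces at mid-range SD. The dropout allowance needs 20/0.85 = 23.5, so 24 patients. Taken by arm it needs 7/0.85 = 8.2, so 9, and 13/0.85 = 15.3, so 16, giving 25. Recruiting 30 leaves 5 to 6 spare.

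**2. Does the stated method deliver 10:20?** With NBOT count X ~ Binomial(30, 1/3):
- P(X = 10) = C(30,10) × 2²⁰/3³⁰ = 15.3%
- central 95% range for X: 5 to 15
- P(X ≤ 8), fewer than the 9 needed for 7 completers: 28.6%
- P(X ≤ 6) = 8.4%

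Fewer than 7 NBOT completers: Binomial(30, 0.85/3) gives 21.2%. With exactly 10 assigned, Binomial(10, 0.85) gives 5.0%.

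**3. What that costs in power.** Exact t, difference 30:

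| Split or scheme | SD 15 | SD 16.5 | SD 18 |
|---|---|---|---|
| 7/13 (plan's requirement) | 98.1% | 95.6% | 91.9% |
| 10/20 | 99.9% | 99.5% | 98.6% |
| 6/24 | 98.8% | 97.0% | 94.1% |
| 5/25 | 97.6% | 94.8% | 90.7% |
| Average, 10:20 fixed, 15% dropout | 99.4% | 98.3% | 96.3% |
| Average, independent draws, 15% dropout | 98.8% | 97.3% | 95.0% |

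The average losses are 0.6, 1.0 and 1.3 points. A 6/24 split still beats 7/13 at every SD, because the HBOT arm grows as the NBOT arm shrinks. The chance that completers give less power than 7/13 is 13.2% under independent draws and 3.5% with 10:20 fixed.

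**4. Foreseeability and baseline order.** No arithmetic applies. The text makes the id the basis of assignment and names no step that hides the result. The order is consent, randomization, evaluation. The Protocol Day 1 list puts the baseline evaluation first, before any session, but does not say that it precedes assignment.

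**The case against.** The strongest reply is that most of this is inferred from silence. Allocation software can apply blocks, and a plan to recruit 10 and 20 is compatible with restricted allocation. The patient id may be a study number issued at enrolment. Randomization comes after consent, and prediction would need a deterministic rule known to recruiters, which the document does not state. The closing line of Adverse Event Reporting refers to an overall study protocol that is not among the documents, so fuller detail may exist. All of this stands. It limits the point to no safeguard being described; the absence of one is not shown.

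Two stronger readings are tempting, and the documents do not support either.

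- **That recruiters can foresee assignments.** A reader might infer this from the word id. It needs an id known beforehand and a known rule, and neither is stated.
- **That the trial could fall below its required power because NBOT may drop under 7.** The requirement is 7 together with 13 HBOT. Fewer than 7 NBOT among 30 is not in itself a shortfall, as 6/24 shows. The 21.2% against 5.0% comparison therefore overstates the loss, and even under independent draws average power stays at about 95% or better.

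The double-blind label does not answer the concern. Blinding concerns knowledge after assignment, concealment concerns knowledge before it, and no blinding method is given. Nor does the objection reach the order of events, which the document states outright.

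**Conclusion.** The concern holds in a limited form. The document bases allocation on patient id, describes no concealment or restriction, and places baseline evaluation after randomization. The main risk is selection bias and baseline-assessment bias in a trial with about 10 controls. Its size cannot be computed from the documents. The selection part is conditional on the id being known before consent and fixing the arm. The ordering part rests on the text as written, although any bias from it also requires that someone involved in the evaluation knows the arm.

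The 10:20 split is not secured. Under independent draws it would be met about 15% of the time, but the price is only about 0.6 to 1.3 points of average power at SD 15 to 18 with 15% dropout. Power alone would not justify the change. The change is worth making because a lapse in concealment cannot be repaired once enrolment has begun.

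**What to change.** In Data Collection Procedures, replace the parenthetical on randomization with:

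> Allocation follows a computer-generated 2:1 list in permuted blocks of varying size (multiples of 3, undisclosed to recruiting staff, constrained to close at 10 NBOT and 20 HBOT at 30 patients), generated before enrolment independently of any patient identifier and concealed from recruiters. The assignment is released only after consent, irrevocable registration and completed baseline evaluation.

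Reword the opening and following sentences so that the order is consent, baseline evaluation, randomization. Changing the parenthetical alone would leave the section contradicting itself.

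The closing constraint is needed because blocks of 3 and 6 in random order need not end at 30. One combination that does is four of 3 and three of 6: 12 + 18 = 30 patients, with 4 × 1 + 3 × 2 = 10 NBOT.

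The cost is a small text change and one list, with no extra patients or procedures. The downside is that small blocks at a single site add some predictability if staff can tell the arms apart. Varying, undisclosed block sizes limit this but do not remove it. If the software already works this way, stating so is enough for the allocation part, and only the order of baseline and randomization needs changing.
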